5.6. Concomitant Medications

5.6.1. Permitted Medications

All concomitant medications and treatments must be recorded in the source document and ideally should remain stable through the end of the treatment portion of the study. All prior medications for CIP and any prior medications received up to 30 days before study enrollment will be recorded in the source document. Concomitant treatments and/or procedures that are required to manage a subject's medical condition during the study will also be recorded in the source document.

5.6.2. Restricted Medications and Measures

- Use of any over-the-counter, nonprescription preparations (including vitamins, minerals, and phytotherapeutic, herbal, or plant derived preparations) within 7 days before the baseline visit, unless deemed acceptable by the investigator.
- Use of any prescription medication (including immunizations, phytotherapeutic, herbal, or plant-derived preparations) within 14 days before the baseline visit, unless deemed acceptable by the investigator.
- Use of anti-histamines, doxepin, gabapentin, etc. and other treatments for pruritus should be eliminated at screening.
- Mild-to-moderate CYP3A4 inhibitors will be discouraged from use.

5.6.3. Prohibited Medications and Measures

The following medications are not permitted during the study:

- Any investigational medication other than the study drugs.
- Corticosteroids, topical corticosteroids.
- Other topical agents for chronic pruritus (including topical moisturizers).
- Systemic corticosteroids, methotrexate, cyclosporine A, azathioprine and biological therapies, or other immunosuppressant agents.

- Leukotriene inhibitors, calcineurin inhibitors.
- Allergen immunotherapy.
- Phototherapy or tanning beds.
- Live or live-attenuated vaccination.
- Cytochrome 450 enzyme inducers (rifampin, phenobarbital, carbamazepine, phenytoin)

6. STUDY ASSESSMENTS

All study assessments will be performed as indicated in the schedule of assessments **Table 1**, in the order listed, and all laboratory assessments will be performed as indicated in **Table 2**:

Table 1: Schedule of Assessments

Evaluation	Screening	Treatment						Follow-Up
	Day -28 to -1	Baseline	Week 2 Day 14 \pm 3 Days	Week 4 Day 28 \pm 3 Days	Week 8 Day 56 \pm 3 Days	Week 12 Day 84 \pm 3 Days	Week 16 Day 112 \pm 3 Days	Week 18 Day 96 \pm 3 Days
Clinic visit	X	X	X	X	X	X	X	X
Informed consent	X							
Inclusion/exclusion criteria	X	X						
Demography and medical history	X							
Prior/concomitant medications	X	X	X	X	X	X	X	X
Height and body weight	X							
Comprehensive physical exam	X							
Targeted physical exam (if indicated)		X	X	X	X	X	X	X
Vital signs and weight	X	X	X	X	X	X	X	X
Laboratory assessments	X						X	
Chest x-ray	X							
Hepatitis screening tests	X							
Pregnancy test ^a	X	X	X	X	X	X	X	X
Efficacy assessment (NRS itch score)	X	X	X	X	X	X	X	X
Derm Quality of Life Index	X	X	X	X	X	X	X	X
Study drug dispensed/Collect study drug bottles		X	X	X	X	X	X	
Assess compliance			X	X	X	X	X	
Skin biopsy RNA-seq transcriptional profile, and Histopathological analysis		X					X	
Assess AEs	X	X	X	X	X	X	X	X

^aAll women will have a serum pregnancy test conducted at the screening visit and urine pregnancy tests conducted at all other visits (including baseline) unless postmenopausal (defined as >12 months from last menstrual period) or surgically sterile)

Table 2: Clinical Laboratory Assessments

Serum Chemistries	Hematology
Albumin Alkaline phosphatase ALT AST Bicarbonate Blood urea nitrogen Calcium Chloride Creatinine Glucose Phosphorus Potassium Sodium Total bilirubin Total serum protein	Hematocrit Hemoglobin Mean corpuscular volume Platelet count Red blood cell count Reticulocyte count White blood cell count White blood cell differential (5 part): 
 • Basophils • Eosinophils • Lymphocytes • Monocytes • Neutrophils
Other	Serology
ESR Lactate dehydrogenase Urinalysis Urine pregnancy test (at site) Serum pregnancy test TSH	Hepatitis B surface antigen Hepatitis C virus antibody HIV p25 antigen

6.1. Screening

Screening is the interval between the signing of the ICF and the day the subject receives the first dose of the study drug. Informed consent must be obtained before performing any study-specific procedures. Assessments that are required to demonstrate eligibility may be performed over the course of 1 or more days during screening.

Results from the screening evaluations will be reviewed to confirm subject eligibility before administration of study drug. Tests with results that fail eligibility requirements may be repeated once during screening if the investigator believes the results to be in error. Additionally, a subject who fails screening may repeat the screening process one

time if the investigator believes that there has been a change in eligibility status (eg, following recovery from an infection).

6.2. Baseline

The results from the screening evaluations will be reviewed to determine if the subject continues to meet the eligibility requirements as specified in the Protocol.

Subjects who have signed the ICF and meet all the entry criteria may be enrolled in the study.

6.3. Treatment

Subjects who meet all the study entry criteria and none of the exclusion criteria will return to the study site on Day 1 of administration. Dates for subsequent study visits will be determined based on this day and should occur within the visit windows outlined in the schedules of assessments.

The treatment period begins when the subject receives their first dose of study drug, which will be administered in the clinic. A one month supply will be dispensed to subjects with detailed instructions.

6.4. End of Treatment

If a decision is made that the subject will permanently discontinue study drug, the EOT visit should be conducted. If the EOT visit coincides with a regular study visit, the EOT evaluations will supersede those of that scheduled visit, and the data should be entered in the EOT page in the source document. The subject should be encouraged to return for the follow-up visits.

6.5. Follow-Up

Subjects will have follow-up assessments two weeks after the last dose of study drug. If prohibited treatment for CIP is started, an earlier follow-up visit may be performed. A final and thus end-of-study visit should be performed, ideally no earlier than 14 days after the last dose of study drug. Adverse events and SAEs must be reported up until at least 14 days after the last dose of study drug, the date of the follow-up visit, or until toxicities resolve, return to baseline, or are deemed irreversible, whichever is longer. Reasonable efforts should be made to have the subject return for the follow-up visits and report any AEs that may occur during this phase.

6.6. Unscheduled Visits

Unscheduled study visits may occur at any time if medically warranted. Any assessments performed at those visits should be recorded in the source document. If there is worsening of CIP at an unscheduled visit, then NRS and DLQI scores should be obtained and documented.

6.7. Early Termination

In the event that any subject discontinues the study drug and subsequently the study prior to completion, regardless of reason, reasonable efforts should be made to have the subject return for an early termination visit and have the EOT procedures completed as noted.

Subjects who are noncompliant with study drug (defined as < 80% compliant based on number of tablets) will have the administration instructions reinforced by the investigator or a qualified designee. After reinforcement, subjects who again fail to meet 80% compliance benchmarks in a subsequent visit will be considered for withdrawal from the study.

7. CONDUCT OF STUDY ASSESSMENTS AND PROCEDURES

7.1. Administration of Informed Consent Form

Valid informed consent must be obtained from the study subject before conducting any study-specific procedures using an ICF approved by the local IRB/IEC that contains all elements required by ICH E6, and describes the nature, scope, and possible consequences of the study in a form understandable to the study subject. Local and institutional guidelines for ICF content and administration must be followed; the original signed ICF must be retained by the investigator, and a copy of the signed ICF must be provided to the study subject. The informed consent process for each subject must be documented in writing within the subject source documentation.

7.2. Demography and Medical History

7.2.1. Demographics and General Medical History

Demographic data and general medical history will be collected at screening.

7.2.2. Disease Characteristics and Treatment History

A disease-targeted medical and medication history will be collected at screening.

7.3. Prior and Concomitant Medications and Procedures

Prior and concomitant medications and procedures will be reviewed to determine subject eligibility. All concomitant medications and measures must be recorded in the source document, and any medication received or procedure performed within 30 days before randomization and up to the end of study will be recorded in the source document. The medication record will be maintained after signing the ICF to document concomitant medications, including any changes to the dose or regimen. Concomitant medications include any prescription, over-the-counter, or natural/herbal preparations taken or administered during the study period. Concomitant treatments and/or procedures that are required to manage a subject's medical condition during the study will also be recorded in the source document.

7.4. Safety Assessments

7.4.1. Adverse Events

Adverse events will be monitored from the time the subject signs the ICF. Subjects will be instructed to report all AEs during the study and will be assessed for the occurrence of AEs throughout the study. In order to avoid bias in eliciting AEs, subjects will be asked general, nonleading questions such as "How are you feeling?" All AEs (serious and nonserious) must be recorded in the source document regardless of the assumption of a causal relationship with the study drug. The definition, reporting, and recording requirements for AEs are described in Section 8.

7.4.2. Physical Examinations

Physical examinations must be performed by a medically qualified individual such as a licensed physician, physician's assistant, or an advanced registered nurse practitioner, as local law permits.

Clinically notable abnormalities that are considered clinically significant in the judgement of the investigator are to be reported as AEs.

7.4.2.1. Comprehensive Physical Examination

The comprehensive physical examination will include height (at screening) and body weight, and assessment(s) of the following organ or body systems: skin; head, conjunctivae, oral mucosa; thyroid; lungs; cardiovascular system; abdomen (liver, spleen); extremities; and lymph nodes; as well as a brief neurological examination.

7.4.2.2. Targeted Physical Examination

The targeted physical examination beyond screening and baseling will be conducted at discretion of investigator as indicated and will a symptom-directed evaluation. The targeted physical examination will include assessment(s) of the body systems or organs, as indicated by subject symptoms, AEs, or other findings.

7.4.3. Vital Signs and Weight

Vital sign measurements include blood pressure, pulse, respiratory rate, and body temperature. Blood pressure and pulse will be taken with the subject in the recumbent, semirecumbent, or sitting position after 5 minutes of rest. Subjects will be weighed at each visit. Clinically notable abnormalities that are considered clinically significant in the judgment of the investigator are to be reported as AEs.

7.4.4. Electrocardiograms

N/A.

7.4.5. Laboratory Assessments

Clinical laboratory tests will be performed using a central laboratory. A detailed description of the procedures for sampling, handling, storage, and shipment of the

central laboratory samples and all material such as test tubes and labels is provided in the central Laboratory Manual. If unscheduled local laboratory tests are performed and those results lead to a dose modification, delay, or dose interruption, or any additional non-Protocol-required test is performed because of an AE, those results and the normal reference ranges for those analytes must be documented in the source document. Otherwise, unscheduled local laboratory test results need not be entered in the source document.

Tests required at each visit are shown in Table 1. Additional analytes may be requested based on emerging data, if indicated for safety of study subjects. In addition, some subjects may receive additional assessments as medically indicated; results of nonrequired tests may also be entered in the source document.

7.4.5.1. Chemistry, Hematology and Urinalysis

A panel of standard serum chemistries, hematology, urinalysis will be analyzed at screening and Visit 16 (EOT). All serum chemistries will be performed from blood samples collected without respect to food intake (ie, nonfasting).

7.4.5.2. Hepatitis Screening

Hepatitis test in Table 2 will be conducted during screening period in order to best interpret liver function test abnormalities that may develop during the course of the study. It is therefore not mandatory that this result be available before enrollment (day one) if clinical evaluation and medical history provide not reason to suspect ongoing active or subclinical hepatitis infection.

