3. SUBJECT ELIGIBILITY

Deviations from eligibility criteria are not allowed because they can potentially jeopardize the scientific integrity of the study, regulatory acceptability, and/or subject safety. Therefore, adherence to the criteria as specified in the Protocol is essential.

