3.2. Subject Exclusion Criteria

A subject who meets any of the following criteria will be excluded from the study:

1. Chronic pruritus due to a defined primary dermatologic disorder (e.g., atopic dermatitis, psoriasis, etc.).
2. Patients with a prior diagnosis of excoriation disorder.
3. Use of topical treatments for CIP (other than bland emollients) within 1 week of baseline.
4. Subjects receiving systemic immunosuppressive or immunomodulating drugs (eg, oral or injectable corticosteroids, methotrexate, cyclosporine, mycophenolate mofetil, azathioprine) within 4 weeks of Baseline.
5. Subjects with cytopenias at screening, defined as:
 - a. Leukocytes $< 3 \times 10^9/L$
 - b. Neutrophils $<$ lower limit of normal
 - c. Lymphocytes $< 0.5 \times 10^9/L$
 - d. Hemoglobin < 10 g/dL
 - e. Platelets $< 100 \times 10^9/L$
6. Unwilling or unable to follow medication restrictions or unwilling or unable to sufficiently washout from use of restricted medication or under treatment for skin disease with therapy listed in prohibited medications that may influence results of this study.
7. Use of any prohibited medications (see Section 5.6.3) within 14 days or 5 half-lives (whichever is longer) of the Baseline visit.
8. Current clinically significant cardiovascular, respiratory, neurologic, hepatic, hematopoietic, renal gastrointestinal, endocrine or metabolic dysfunction unless currently controlled and stable, including (but not limited to) the following:
 - a. Positive for hepatitis C antibody test (anti-HCF);
 - b. Positive for hepatitis B surface antigen (HBsAg) or hepatitis B core antibody (HBcAb);
 - c. Positive for HIV (DUO test, p24 antigen)

9. Active malignancy.
10. History (including family history) or current evidence of congenital long QT syndrome or known acquired QT prolongation.
11. Exposure to any investigational medication, including placebo, within 60 days of the Baseline Visit.
12. History of intolerance and/or hypersensitivity to medications similar to apremilast.
13. Subjects with prior treatment with apremilast.
14. Subjects with severely impaired liver function (Child-Pugh Class C) or end-stage renal disease on dialysis or at least 1 of the following:
 - a. Serum creatinine > 1.5 mg/dL;
 - b. Alanine aminotransferase or aspartate aminotransferase $\geq 1.5 \times$ upper limit of normal
15. Anyone affiliated with the site or sponsor and/or anyone who may consent under duress.

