4. INVESTIGATIONAL PLAN

4.1. Overall Study Design

This study is an open label pilot study examining the efficacy of apremilast in the treatment of CIP. Ten (10) subjects who meet the eligibility criteria are planned to be enrolled. The total duration of subject participation will be 6 study visits over approximately 16 weeks. All subjects will receive apremilast 30 mg by mouth BID for 16 weeks.

All apremilast subjects will have visits at Screening, Baseline, and Weeks 2, 4, 8, 12, 16, and 18 (follow-up). Adverse events (AEs), medication history, clinical assessments, physical exam, and vital signs will be performed at each visit. Clinical safety laboratories will be performed at screening and Week 16 (EOT). All laboratory assessments will be performed using The Barnes-Jewish Hospital laboratory except for urine pregnancy tests (as applicable). NRS and DLQI scoring will be performed by a research nurse.

Two skin biopsies will be performed at the most pruritic site at Baseline and at Week 16 (adjacent to the initial biopsy site) for histopathological analysis and RNA-seq transcriptional analysis.

After the end-of-treatment visit (Week 16, or early termination), subjects will have follow-up assessments two weeks later (week 18) to monitor for durability of effect (relapse rate), AEs, medication history, vital signs, and clinical assessments.

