4.4. Duration of Treatment and Subject Participation

After signing the ICF, screening assessments may be completed over a period of up to 28 days. Scheduled study visits are at Week 2, 4, 8, 12, and 16. Follow up is at Week 18.

Study participation is expected to be approximately 18-22 weeks per individual subject with variance related to screening process duration.

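### Section 7.4.5.2 allows dosing on Day 1 before hepatitis results are known, and Table 2 has no test for the hepatitis B core antibody that exclusion 8b relies on

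*Combined protocol and SAP*

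**What the plan says.** Exclusion 8 in Section 3.2 names three hepatitis markers. Item 8a bars a positive hepatitis C antibody. Item 8b reads "Positive for hepatitis B surface antigen (HBsAg) or hepatitis B core antibody (HBcAb". The synopsis repeats both.

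The tests meant to detect these are the hepatitis tests of Table 2, scheduled once, at screening (Table 1). The Serology cell of Table 2 reads "Hepatitis B surface antigen Hepatitis C virus antibody HIV p25 antigen". HBcAb does not appear anywhere in the table.

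Section 7.4.5.2 gives the purpose of the hepatitis test as helping to interpret liver abnormalities that arise later in the study. It then says "It is therefore not mandatory that this result be available before enrollment (day one) if clinical evaluation and medical history" raise no suspicion of active or subclinical hepatitis.

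Three other places set a stricter rule:

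- Section 3: "Deviations from eligibility criteria are not allowed".
- Section 6.1: "Results from the screening evaluations will be reviewed to confirm subject eligibility before administration of study drug".
- Section 6.3: "Subjects who meet all the study entry criteria and none of the exclusion criteria will return to the study site on Day 1". The same section places the first dose in the clinic.

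On liver monitoring, Section 4.1 says "Clinical safety laboratories will be performed at screening and Week 16 (EOT"). Table 1 and Section 7.4.5.1 agree.

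**The concern.** The protocol gives hepatitis serology two incompatible roles. In exclusion 8 it decides eligibility, so the result is needed before dosing. In 7.4.5.2 it is background for reading later liver tests, so the result can come afterwards. Because 7.4.5.2 is the specific rule for this test, a site could reasonably follow it over the general rule in 6.1. It would then dose someone whom Section 3 says may not be enrolled.

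The waiver applies to subjects in whom infection is not suspected clinically. Those are the subjects in whom only serology would reveal it. For HBcAb the problem goes beyond timing, because no result is ever produced.

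What is at stake is subject safety and the integrity of eligibility. The efficacy estimate is not in question.

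**Working it through.** The plan states no figure to reproduce. The check sets the provisions side by side.

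**1. Markers that exclude, against markers that are tested**

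| Marker | Exclusion (3.2) | In Table 2? | Result required before Day 1? |
|---|---|---|---|
| Hepatitis C antibody | 8a | Yes | Not if unsuspected (7.4.5.2) |
| HBsAg | 8b | Yes | Not if unsuspected (7.4.5.2) |
| HBcAb | 8b | No | No result exists |

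Two of the three markers are tested, and both may be reported late. One of the three is not tested.

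**2. Whether a late result means a dosed subject.** Section 7.4.5.2 ties the waiver to day one, and Section 6.3 puts the first dose on that day. A subject enrolled under the waiver is therefore dosed before the result is seen. Sections 3, 6.1 and 6.3 do not permit this, so the two sets of rules cannot both be followed.

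**3. Scheduled liver tests after the first dose.** ALT and AST belong to the Table 2 chemistry panel, which is drawn at screening and Week 16.

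- On-treatment visits before Week 16: Weeks 2, 4, 8 and 12. Visits with scheduled chemistry: 0 of 4.
- Week 16 is Day 112 ± 3: 112 − 3 = 109 and 112 + 3 = 115.
- Gap from Day 1: 112 − 1 = 111 days, with a range of 109 − 1 = 108 to 115 − 1 = 114.

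Section 5.4.2 interrupts dosing when ALT or AST exceeds 3 × ULN. Before Week 16 only an unscheduled test, or the end-of-treatment visit of a subject who stops early, could trigger that rule.

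**4. Who remains exposed.** Exclusion 14b removes anyone with ALT or AST at or above 1.5 × ULN at screening, whatever the serology. Among subjects below that level, two groups remain:

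- those positive for HBcAb only, whom no listed test identifies;
- those with unsuspected positive HBsAg or hepatitis C antibody whose result arrives after the first dose. They are exposed at least until it arrives.

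**The case against.** The strongest case on the other side accepts the text but limits its consequence.

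- **Late positives can be acted on.** Section 7.4.5.2 still has the test done during screening, so only the result is late. Section 5.5.1 lets the investigator withdraw a subject later found ineligible. For HBsAg and hepatitis C antibody, exposure before anyone can act therefore lasts until the result arrives and need not run to Week 16. This stands as a limit on duration. However, 5.5.1 is discretionary, works only after dosing, and cannot help with a marker that is never tested.
- **No liver hazard is shown.** The protocol reports that moderate or severe hepatic impairment does not alter apremilast pharmacokinetics (1.6.1). It also reports no excess of serious infections and no Hy's Law cases (1.6.3). These data do not address viral hepatitis, but they do mean the documents support no claim of hepatotoxicity or reactivation. None is made here; the point is that the protocol's own exclusion cannot be applied reliably.
- **Exclusion 8 is loosely worded.** Items 8a to 8c sit under a stem that exempts controlled, stable conditions, so isolated HBcAb positivity could be read as not excluding. The natural reading is that a positive test excludes. The ambiguity is a reason to clarify the text.
- **The laboratory schedule is a separate choice.** This is fair. The Week 16 gap is context for the missing safeguard, and the fix leaves it alone. Section 7.4.5 also allows extra tests when medically indicated, though it does not require them.

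**Conclusion.** The concern holds. Followed as written, Section 7.4.5.2 and Table 2 can lead to dosing a subject who meets exclusion 8a or 8b. One of the three named markers has no test, and the other two may be reported after the first dose when infection is not suspected. The next scheduled ALT and AST fall at Day 109 to 115.

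This rests on two readings: that a positive result under 8a or 8b excludes in itself, and that a site would apply the specific rule in 7.4.5.2 over the general rule in 6.1. If 6.1 is taken to govern, the waiver serves no purpose and should go; the missing HBcAb test remains either way.

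The documents give no prevalence, so the expected number among the ten planned subjects cannot be stated. The point is minor in weight, but correcting it improves subject safety.

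**What to change.** 1. In Section 7.4.5.2, replace the sentence that waives the result with: *Hepatitis B (HBsAg, HBcAb) and hepatitis C antibody results must be available and reviewed against exclusion 8 before the first dose.*
2. In Table 2, Serology, add hepatitis B core antibody.
3. As tidying edits, list 8a to 8c in Section 3.2 and the synopsis as a separate exclusion, outside the exemption for controlled and stable conditions. Also change the p25 entry in Table 2, probably a typing error, to the p24/DUO test named in 8c. The timing of the HIV result is not in question, since 6.1 applies to it without exception.

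Section 5.5.1 needs no change.

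The cost is the text edits, one added serology test per person screened, and possibly a few more screen failures. Section 4.4 says "screening assessments may be completed over a period of up to 28 days", which leaves time to obtain the results before Day 1. No visit is added.
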